#### 14.5. Primary Analysis

The two primary endpoints, changes of axial length (AL) and cycloplegic auto refraction (SECAR) from baseline at 6 months follow-up, will be analyzed separately using a linear mixed model for longitudinal data. Each model will include treatment group, time period (in weeks) and treatment group by time interaction as fixed effect factors; and site, subject nested in site, and eye nested in subject as random effect factors when appropriate. Other baseline characteristics known of importance such as age, gender, refractive error at baseline, axial length at baseline, pupil size, parental history of myopia and other factors will be included as fixed covariates when appropriate. The covariance between residual errors from the same subject/eye across lens wearing time periods will be selected based on the finite-sample corrected Akaike's Information Criterion. Covariance structures considered may include: Homogeneous Compound Symmetry (CS), first-order autoregressive (AR(1)) and Unstructured covariance structure (UN). For AR (1) structure, site, subject nested in site and eye nested in subject will be included in each model as random effects. For the remaining structures, only site and subject will be included as random effects. The covariance structure that returns the lowest Akaike Information Criteria Corrected (AICC) will be selected as the structure that best fit the data. Heterogeneous residuals covariance structures (R-side) across treatment groups will be considered when appropriate. The log-likelihood ratio test will be

used to test for the homogeneity between the residual covariance structures. The Kenward and Roger method will be used for the denominator degree of freedom.

The null and alternative hypotheses for superiority for each test lens relative to the control are as follows for AL and SECAR:

$$H_0: \Delta_{AL} \ge 0; H_A: \Delta_{AL} < 0;$$
$$H_0: \Delta_{SECAR} \ge 0; H_A: \Delta_{SECAR} < 0,$$

where  $\Delta_{AL}$  and  $\Delta_{SECAR}$  are the mean differences (Test minus Control) in change from baseline of AL and SECAR at 6 months follow-up respectively.

For each primary endpoint, the comparison between the treatment groups at 6-Month time period will be conducted using a t-test on least-square means from the final model. The corresponding CI of least-square mean (LSM) difference (i.e. LSM change from baseline of test group minus LSM change from baseline for control group) will be calculated with 95% confidence to test the primary hypothesis.

Superiority of the test lens relative to the control lens in reducing change from baseline in axial length at 6-Month will be claimed if the corresponding upper confidence limits of the LSM differences is smaller than 0.

Superiority of the test lens relative to the control lens in reducing the magnitude of change from baseline in cycloplegic auto refraction at 6-Month will be claimed if the corresponding lower confidence limits of the LSM differences is greater than 0.

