#### 2.2. Endpoints

#### **Primary Endpoints**

There are two co-primary endpoints in this study:

- 1. Change of axial length (AL) from baseline at 6 months;
  - Axial length (in the unit of mm) will be measured using LENSTAR LS 900 manufactured by Haag-Streit, or a similar device (e.g., IOLMaster) in selected Asian sites upon approval of the sponsor.
- 2. Change of spherical equivalent of cycloplegic auto refraction (SECAR) from baseline at 6 months

SECAR (in the unit of D) will be computed from the sphero-cylindrical refraction measured by a commercially available autorefraction such as WAM-5500 manufactured by Grand Seiko.

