#### 2.3. Hypotheses

#### Primary Hypotheses:

After approximately 6 months of lens wear, at least one of the three Test lenses (EMO-114, -116, and -118) will be efficacious in slowing the progression of myopia compared to the Control lens (EMO-117) such that:

- 1. the change of axial length (AL) of the eye from baseline will be statistically significantly less for the Test lens compared with the Control lens.
- 2. the change of Spherical Equivalent of Cycloplegic Auto Refraction (SECAR) of the eye from baseline will be statistically significantly less in magnitude with the Test lens compared with the Control lens.

Both conditions regarding the performance of the Test lens must be met in order to meet the primary objective.

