#### 3.2. Inclusion Criteria

Potential subjects must satisfy all of the following criteria to be enrolled in the study:

Inclusion Criteria after Screening:

- 1. The subject must read (or be read to), understand, and sign the Statement of Information and Assent and receive a fully executed copy of the form.
- 2. The subject's parent(s) or legal guardian(s) must read, understand and sign the Statement of Informed Consent and receive a fully executed copy of the form.
- 3. Appear able and willing to adhere to the instructions set forth in this clinical protocol.
- 4. Between 7 and 12 years of age (inclusive).
- 5. Have normal eyes (i.e., no ocular medications or infections of any type).

Inclusion Criteria after Baseline 1:

- 6. Distance subjective best-sphere refraction must be between -0.75D and -4.50D (inclusive) in each eye.
- 7. Cylindrical refraction must be 1.00D or less in each eye, by subjective sphero-cylindrical refraction.
- 8. Have sphero-cylindrical best-corrected visual acuity of 20/25 (ie, 0.8 in decimal convention or 0.10 logMAR) or better in each eye.

Inclusion Criteria after Baseline 2:

- 9. Cycloplegic objective sphero-cylindrical refraction (by auto refraction) must be between -0.75D and -4.50D in sphere and is 1.00D or less in cylinder in each eye (based on the average of 5 repeated sphero-cylindrical refraction measures).
- 10. The difference in spherical equivalent power between the two eyes must be less than 1.50D (based on the average of 5 repeated sphero-cylindrical refraction measures).

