#### 14.2. Sample Size Justification

This is a pilot study for assessing the investigational test articles. As such, the sample size was not determined based on any power analysis with regard to the primary endpoint. The collected data will be used to design future trials. Below sample size calculation is for reference only.

Using the POWER procedure in SAS 9.4, below is the summary of different statistical powers based on the different assumptions of the true difference in each of the primary endpoint at the given sample size (40 per arm). The estimated standard deviation is from the change at 6 months for the test group of the historical study The power analysis was conducted controlling 2-sided type I error of 0.05.

Assuming the true difference in change of axial length (AL) from baseline at 6 months is between 0.05mm to 0.12mm, the table below demonstrates the table below demonstrates the power analysis for the given sample size (40 per arm).

	Estimated Standard		
Difference (Test-Control)	Deviation	# of subjects per arm	Power
0.05	0.10	40	0.60
0.08	0.10	40	0.94
0.10	0.10	40	0.99
0.12	0.10	40	0.99

Assuming the true difference in change of spherical equivalent of cycloplegic auto refraction (SECAR) from baseline at 6 months (in magnitude) is between 0.10D to 0.25D, the table below demonstrates the power analysis for the given sample size (40 per arm).

	Estimated Standard		
Difference (Test-Control)	Deviation	# of subjects per arm	Power
0.10	0.32	40	0.03
0.15	0.32	40	0.54
0.20	0.32	40	0.79
0.25	0.32	40	0.93

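### Section 14.5 states the SECAR alternative hypothesis in the opposite direction to its own rule for claiming superiority

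*Combined protocol and SAP*

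**What the plan says.** Section 14.5 (Primary Analysis) gives the axial length (AL) hypotheses as "H_0: \Delta_{AL} \ge 0; H_A: \Delta_{AL} < 0" and the SECAR hypotheses in identical form, "H_0: \Delta_{SECAR} \ge 0; H_A: \Delta_{SECAR} < 0". The two deltas "are the mean differences (Test minus Control) in change from baseline of AL and SECAR at 6 months follow-up respectively".

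The same section then builds a 95% confidence interval for the least-squares mean difference, again Test change minus Control change, as the test of the primary hypothesis. AL superiority requires the upper limit to be below 0. SECAR superiority "will be claimed if the corresponding lower confidence limits of the LSM differences is greater than 0".

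On scale, Section 2.2 says: "SECAR (in the unit of D) will be computed from the sphero-cylindrical refraction measured by a commercially available autorefraction". Inclusion criterion 9 in Section 3.2 shows the sign convention, since cycloplegic refraction "must be between -0.75D and -4.50D in sphere and is 1.00D or less in cylinder in each eye".

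Section 2.3 makes SECAR decisive: "Both conditions regarding the performance of the Test lens must be met in order to meet the primary objective". Sections 2.3, 14.2 and 14.5 all describe the SECAR effect in terms of magnitude; Section 14.2, for example, takes a true difference in change "from baseline at 6 months (in magnitude) is between 0.10D to 0.25D". No section says that an absolute value is computed.

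**The concern.** The hypothesis line and the claim rule concern the same contrast and point in opposite directions. A confidence interval wholly above 0 satisfies the claim rule but lies entirely inside the stated null hypothesis. For AL the two statements agree, so the inconsistency is confined to SECAR.

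SECAR is one of two endpoints that must both succeed. If the analysis were programmed from the stated alternative on signed change, an effective lens would fail SECAR and with it the primary objective. A lens that speeds progression could pass SECAR.

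**Working it through.** **1. Sign check (illustrative values).** Suppose the mean 6-month change is −0.40 D on Control and −0.20 D on Test, so Test halves the progression.

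- Signed scale: −0.20 − (−0.40) = +0.20 D.
- Absolute scale: 0.20 − 0.40 = −0.20 D.

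| Scale | Benefit means | Stated alternative (< 0) | Claim rule (lower limit > 0) |
|---|---|---|---|
| Signed dioptres | difference > 0 | wrong direction | right direction |
| Absolute change | difference < 0 | right direction | wrong direction |

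The two statements conflict on either scale. The signed scale is the one the document supports: SECAR is in dioptres (Section 2.2), myopia is recorded as negative (Section 3.2), and delta is defined on plain change from baseline with no transformation (Section 14.5). The power tables in Section 14.2 do not settle the sign. Their Test-minus-Control column is positive for AL as well, where benefit is negative, so the entries are sizes only.

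**2. Inputs.** Section 14.2 gives SD 0.32 D (SECAR) and 0.10 mm (AL), 40 per arm, two-sided alpha 0.05. The 95% interval is from Section 14.5. As an approximation to the mixed model, I use a two-sample t-test with 78 degrees of freedom.

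**3. Reproducing the plan's power.** For SECAR, SE = 0.32 × √(2/40) = 0.0716. Power comes from the noncentral t distribution with noncentrality d/SE.

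| True difference (D) | Computed | Section 14.2 |
|---|---|---|
| 0.10 | 0.28 | 0.03 |
| 0.15 | 0.54 | 0.54 |
| 0.20 | 0.79 | 0.79 |
| 0.25 | 0.93 | 0.93 |

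Three of the four rows reproduce. The 0.03 at 0.10 D does not; it may be a typing error and is a separate matter that does not affect this point.

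**4. One observed result.** The 95% half-width is 1.991 × 0.0716 = 0.142. An observed +0.20 D has the interval 0.20 ± 0.142, that is 0.058 to 0.342. It meets the claim rule and contradicts the stated alternative.

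**5. Probability of success by direction, for a true benefit on the signed scale.**

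| True benefit (D) | P(lower limit > 0), claim rule | P(upper limit < 0), stated alternative |
|---|---|---|
| 0.10 | 0.281 | 0.00042 |
| 0.15 | 0.544 | 0.00003 |
| 0.20 | 0.788 | 0.000001 |
| 0.25 | 0.932 | < 0.000001 |

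**6. The reverse error.** By symmetry, a lens truly 0.20 D worse than Control would pass SECAR in the stated direction with probability 0.788. It must also pass AL. With SE = 0.10 × √(2/40) = 0.0224, the chance that the AL upper limit falls below 0 is 0.025 if the true AL difference is 0, and 0.000015 if it is +0.05 mm. The joint probability of passing both cannot exceed these AL values, whatever the correlation between the endpoints.

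**The case against.** The strongest reply is that the rule that decides the claim is already prespecified and is correct. Section 14.5 defines the contrast in words, ties the interval to the primary hypothesis, and gives SECAR a different criterion from AL, which suggests that the author had thought about the sign of dioptres. Section 2.3 states the intended direction in words. Only one symbolic line dissents, and it reads like a copy of the line above. The low success probabilities in step 5 belong to a criterion (SECAR upper limit below 0) that the plan never states as a decision rule. Following the rule as written has no adverse effect. The trial is also described as a pilot, not sized by power (Section 14.2).

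Most of this stands, and it limits the weight of the point. An analyst who applies the claim rule to signed change reaches the right conclusion, and the rule leaves little real room to choose a direction after unmasking. That the hypothesis line is the wrong half is an inference from the scale and the sign convention, though a strong one.

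The contradiction itself remains. The repeated references to magnitude, with no stated transformation, give a reader some ground to take the hypothesis line as intended and the rule as the slip. A late correction would also have to be reported and justified as a change to the analysis under Section 14.10.

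**Conclusion.** The concern holds. The formal alternative for a co-primary endpoint is reversed relative to the claim rule in the same section, and no result can satisfy both. On signed dioptres the claim rule is right and the hypothesis line is wrong.

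The consequence depends on which statement is used. Under the claim rule nothing is lost: power is 0.54, 0.79 and 0.93 at true benefits of 0.15, 0.20 and 0.25 D, as the plan states. Under the stated alternative, an effective lens would have at most a 0.0004 chance of passing SECAR across benefits of 0.10 to 0.25 D. A false overall success is largely blocked by the AL requirement. These figures assume SD 0.32 D for SECAR and 0.10 mm for AL, 40 per arm, and a two-sample t approximation.

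This should be fixed before unmasking, but it does not invalidate the design.

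**What to change.** In Section 14.5, restate the SECAR hypotheses as H0: Δ_SECAR ≤ 0 against HA: Δ_SECAR > 0. Add one sentence, there or in Section 2.2, that SECAR change is analysed in signed dioptres, that a negative change means progression, and that no absolute value is taken. Keep the existing SECAR claim rule. The references to magnitude can then stay as plain-language description.

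The cost is one corrected line and one added sentence, made before unmasking. Alpha, sample size, power and data collection are unaffected.

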#### 14.6. Secondary Analysis

Secondary endpoint – serious and significant ocular adverse events will be summarized descriptively using all available data from the entire study, including data from unscheduled visits.

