#### Secondary Hypothesis:

Secondary endpoint and all other safety endpoints will be summarized descriptively. No secondary endpoint hypothesis testing will be performed.

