# 4. STUDY DESIGN AND RATIONALE

#### 4.1. Description of Study Design

This is a multi-site, prospective, randomized, controlled, double-masked, four-arm-parallelgroup, dispensing study.

Each subject will be bilaterally fitted with one of the four types of test articles and wear lenses of the assigned lens type during the entire course of the study. Test articles will be worn a minimum 8 hours per day and 5 days per week (subjects will be encouraged to wear study contact lenses 10 hours or more per day and 7 days per week) in a daily disposable modality for a minimum of 6 months and up to 1 year\*.

There will be a total of 7 scheduled visits. Visit 1: Screening and baseline evaluation Visit 2: Baseline, randomization, lens fit and dispensing Visit 3: 1-week follow-up Visit 4: 1-month follow-up Visit 5: 3-month follow-up Visit 6: 6-month follow-up Visit 7: 1-year follow-up (optional)\*

\* The study will complete after all subjects have completed the 6-month follow-up (Visit 6). Considering the extensive enrollment period (e.g., approximately 8 months), while waiting for the last enrolled subjects to complete the 6-months follow-up, the study allows subjects enrolled at the beginning of the enrollment period to continue wearing study lenses for up to 1 year and complete the 1-year follow-up (Visit 7) before completing the final evaluation and exiting the study.

Study participants will have no access to test articles at study closure.

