	Screening,	Lens Fitting,	Visit 4 (1-month)	Lens	Lens Follow-
	Baseline	Dispensing	Visit 5 (3-months)	Follow-up	up 1-year
			Lens Follow-up	6-months	(Optional)
Time Point	-	Day 0 Within 3 weeks from V1	V3: 7±3 days; V4: 28±7 days; V5: 91±7 days after V2	182±14 days after V2	364±21 days after V2
Estimated Visit Duration	3.5 hours	3.0 hours	2.0 hour	3.0 hours	3.0 hours
Study Lens Removal			X	X	X
Study Completion, Final Evaluation		X		(x)	X

"(x)" indicates procedures if applicable

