#### **14. STATISTICAL METHODS**

#### 14.1. General Considerations

Statistical Analysis will be undertaken by the Sponsor. A general description of the statistical methods to be implemented in this clinical trial is outlined below.

All data summaries and statistical analyses will be performed using the SAS software Version 9.4 (SAS Institute, Cary, NC). Throughout the analysis of data, the results for each subject/eye will be used when available for summarization and statistical analysis. Unscheduled visits will be summarized separately and will be excluded from the statistical analysis.

Summary tables (descriptive statistics and/or frequency tables) will be provided for all baseline variables, efficacy variables and safety variables as appropriate. Continuous variables will be summarized with descriptive statistics (n, mean, standard deviation (SD), median, minimum and maximum). Frequency count and percentage of subjects or eyes within each category will be provided for categorical data.

All statistical analysis will be conducted on the per-protocol population defined in section 14.3.

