#### 14.3. Analysis Populations

#### **Safety Population:**

All subjects who are administered any test article excluding subjects who drop out prior to administering any test article. At least one observation should be recorded.

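### Serious and significant ocular adverse events are pooled as counts and percentages with no account of time on lens, so the arms are comparable only if early stopping is similar across them

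*Combined protocol and SAP*

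**What the plan says.** Serious and significant ocular adverse events are the only secondary endpoint. Section 14.6 states that they "will be summarized descriptively using all available data from the entire study, including data from unscheduled visits". The general rule in section 14.1 is: "Frequency count and percentage of subjects or eyes within each category will be provided for categorical data". Section 2.3 adds: "No secondary endpoint hypothesis testing will be performed".

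Follow-up is unequal by design. Section 4.1 has lenses worn "in a daily disposable modality for a minimum of 6 months and up to 1 year", and early enrollees may "continue wearing study lenses for up to 1 year". Follow-up visits before month 6 fall at "V3: 7±3 days; V4: 28±7 days; V5: 91±7 days after V2" (Table 3). The safety population in section 14.3 is "All subjects who are administered any test article excluding subjects who drop out prior to administering any test article", with at least one observation recorded. A child fitted at Visit 2 but never dispensed lenses therefore appears to belong to it.

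Lens wear can end for reasons linked to the assigned lens. Randomisation precedes the trial fitting (section 5.1). The acuity, acceptable-vision and fit criteria are applied afterwards (step 2.18), and again before dispensing at Visits 3 to 6. Section 8.2 also lists poor vision, poor comfort, unacceptable fit and insufficient wear time as grounds for withdrawal.

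Section 14.7 lists wear time (item 12) and disposition (item 15) as separate summaries. Neither is linked to the adverse events. Section 14.6 names no population, while section 14.1 says: "All statistical analysis will be conducted on the per-protocol population defined in section 14.3".

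**The concern.** A percentage of children with an event has a clear meaning when all children are watched for about the same time. Here one child may contribute minutes of wear and another 12 months, and each counts once in the denominator. A child who leaves early for blurred vision has little time in which to have an ocular event, yet still dilutes the percentage.

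Section 1.4 says that vision with these designs may not equal that with a conventional spherical lens. Early stopping could therefore be more frequent on a test lens than on EMO-117. In that case the less well tolerated lens would show a lower percentage at the same true rate.

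Safety is the secondary objective, and the overall objective in section 2.1 compares the prototypes with a control. Section 14.2 says the data will be used to design future trials. A percentage that blends 6- and 12-month risk cannot be converted into a rate for that purpose without the exposure behind it.

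**Working it through.** **Inputs from the documents.** Section 6.1 projects up to 60 children per lens type completing 6 months and up to 30 completing 1 year, at about 400 lenses per child per 6 months. The plan's own total reproduces: 60 × 400 + 30 × 400 = 36,000 per lens type, and × 4 = 144,000. This is the only stated figure built on the follow-up split, and it supports taking half of completers to 12 months (30/60).

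**Inputs that are assumptions.** The documents give no dropout by arm, exit time or event rate. I assume:
- half of completers followed to 6 months and half to 12, a mean of 0.5 × 6 + 0.5 × 12 = 9 months;
- early exits at 2 months on average;
- 10% early loss on control;
- 60 treated children per arm, an upper figure;
- the same true rate in both arms, 5 per 100 person-years.

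**Formulas.** With early loss *d*, mean exposure is (1 − *d*) × 9 + *d* × 2 months. For rare events the crude percentage is close to proportional to exposure, so the apparent ratio is test exposure divided by control exposure. Expected events are 60 × exposure/12 × 0.05.

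| Arm and early loss | Mean months | Apparent ratio | Expected events per 60 | Gap |
|---|---|---|---|---|
| Control, 10% | 0.90 × 9 + 0.10 × 2 = 8.30 | – | 2.08 | – |
| Test, 15% | 0.85 × 9 + 0.15 × 2 = 7.95 | 0.96 | 1.99 | 0.09 |
| Test, 20% | 0.80 × 9 + 0.20 × 2 = 7.60 | 0.92 | 1.90 | 0.18 |
| Test, 30% | 0.70 × 9 + 0.30 × 2 = 6.90 | 0.83 | 1.73 | 0.35 |

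In the last row a true excess of 20% would appear as parity (8.30/6.90 = 1.20). If the same 10% and 30% leave at fitting, with no exposure, the ratio is 6.3/8.1 = 0.78.

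**Sensitivity.** A constant-hazard model with 5% loss in one arm gives crude ratios of 0.90 to 0.93 against 15% loss, and 0.71 to 0.81 against 33%, for exits between 1 week and 3 months. Varying the true rate from 2 to 20 per 100 person-years moves these ratios by less than 0.01. Events per person-year return the true rate in both arms.

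**Precision.** For 2 events in 60 × 8.3/12 = 41.5 person-years, the exact 95% Poisson limits on the count are 0.242 and 7.22, or about 0.6 to 17 per 100 person-years. In 498 subject-months that is 0.40 per 100, with limits of about 0.05 and 1.45.

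**The case against.** The strongest reply is that the bias between arms is conditional and small. Section 14.9 says past trials give no evidence of systematic dropout. Base curve, diameter and material are identical across the lenses (section 4.2), so exits for fit should not differ by arm. Section 1 reports satisfactory vision, comfort and fit for EMO-114 and EMO-118. A child who leaves because of a counted event is still counted, so those exits do not lower the percentage. At the assumed rate the distortion is at most about a third of an event per 60 children, in a pilot with no safety test. Disposition and wear time are reported elsewhere, and the wording of sections 14.1 and 14.6 does not forbid a rate.

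Most of this stands, and it limits the point to interpretation. It does not remove it: vision is where the lenses are expected to differ, and a reader given separate tables of disposition and events cannot recover a rate from them.

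The proposed rate is not neutral either. It assumes a roughly constant hazard. If events cluster in early wear, it would inflate the arm with shorter exposure.

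Three stronger readings are tempting:
- *The 6- versus 12-month mix biases the arms.* Time on lens after Visit 6 depends mainly on enrolment date, which 1:1:1:1 block randomisation within site strata should largely balance.
- *The plan expects one third of children to be lost on lens.* The gap between 240 enrolled and 160 completing counts from consent (section 4.3) and so includes screen failures.
- *Early leavers' events will be dropped.* The per-protocol sentence in section 14.1 could be read so, but section 14.6 calls for all available data and section 14.3 defines a safety population. The passages need reconciling; no part of the size above rests on that reading.

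**Conclusion.** The point holds as a reporting weakness of minor weight. The plan ties its adverse-event percentages neither to exposure nor to a fixed window, although exposure runs from the fitting visit to 12 months. The direction is clear if early loss differs by arm: the arm with more of it shows too low a percentage. A reader might go further and infer that a poorly tolerated test lens will look safer than it is. The documents do not support that as a prediction, because they give no dropout by arm. Under the assumptions above the understatement is 4% to 17% in relative terms, or 0.09 to 0.35 of an event per 60 children. If early loss is similar across arms, the comparison stands, and what remains is a percentage that mixes two risk periods and serves planning poorly.

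**What to change.** In section 14.6:
- state that adverse events are summarised in the safety population, and align the sentence in section 14.1 with this;
- keep the planned counts and percentages;
- show months 0-6 separately from the optional extension;
- add, by arm, total lens-wear exposure and serious and significant ocular events per 100 subject-months, with exact Poisson confidence intervals.

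The cost is one further table. Dispensing records, visit dates, wear time and event onset dates are already collected (sections 6.7, 7.2 and 13.3). No procedure, sample size or primary analysis changes. The intervals will be wide with few events, and because of the constant-hazard assumption the rate should be read beside the 0-6-month table, not in its place.
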